## **B1. PURPOSE OF PROTOCOL**

This study aims to compare the efficacy of and outcomes in patients with acute pancreatitis (AP) receiving patient-controlled analgesia (PCA) with those receiving traditional physician-directed analgesia (PDA).

## **B2. SIGNIFICANCE AND BACKGROUND FOR THE STUDY**

AP represents a critical health concern nationwide, with estimated 274,000 admissions annually and at a cost of 2.6 billion dollars. Current treatment strategies for AP are limited to supportive care with fluid resuscitation, analgesia, nutrition and prevention of end organ damage. Abdominal pain is often the predominant symptom in patients with AP and is treated with analgesics. As there is currently no disease-specific medical treatment to change the natural history of pancreatitis, pain control remains central to the treatment of AP (1). Among the analgesics, opioids have been shown to be provide safe and effective pain control in patients with AP. Current literature shows that there is no difference in the risk of pancreatitis complications or clinically serious adverse events between opioids and other analgesia options (2). Among hospitalized AP patients, adequate pain control often requires the use of intravenous (IV) opiates in the first 24-48 hours, which can later be transitioned to oral (PO) opioids. While there are various methods of delivering opioid medications such as IV. PO. and transdermal to name a few, IV opioids are commonly administered, either on a scheduled and/or on an as needed (PRN) basis as directed by the attending physician. In contrast to the conventional, method of physician directed IV opioid delivery, PCA is a form of IV opioid medication delivery in which the patient can rapidly titrate the opioid dose to manage variable levels of pain (3). This modality of opioid administration is often preferred by patients and has been widely used in postsurgical and obstetric patients to effectively treat their pain (4-6). PCA allows for faster intervention on pain limiting time to treatment and peak pain levels and has also been shown to decrease total opioid dose. However, there is limited evidence in published literature assessing the feasibility of using PCA to treat the pain of AP or comparing its efficacy and safety profile compared to the more traditional physician directed analgesia. One retrospective study has shown that use of PCA was surprisingly associated with longer hospital stays and higher rates of outpatient opioid use when compared to PDA, however there are no prospective trials to study this comparison (7). Hence, in this study, we compare the effects of using PCA among patients with AP to that of conventional PDA.

#### **B3. DESCRIPTION OF RESEARCH PROTOCOL**

A. Study Design – Overview, Methods, Procedures

- We will identify patients with AP based on the 2012 revised Atlanta criteria for diagnosis,
   i.e., AP is diagnosed if 2 out of the following 3 criteria are met:
- Acute onset of persistent, severe, epigastric pain often radiating to the back,
- Elevation in serum lipase or amylase to three times or greater than the upper limit of normal,
- Characteristic findings of acute pancreatitis on imaging (contrast-enhanced computed tomography [CT], magnetic resonance imaging [MRI], or transabdominal ultrasonography).
- Patients will be recruited for participation in this study while they are hospitalized with AP at Beth Israel Deaconess Medical Center. Once the patient has been transferred from the ED to the hospital floor, we will identify and recruit them for participation in our study.
- After obtaining informed consent from the patient, the patient will be enrolled by simple randomization to either the PCA or the PDA arm of the study. The research staff will assign patients to either the PCA arm or the PDA arm based on a standard randomization. Once, a patient has consented, the research staff will assign them to the next sequential study ID and corresponding study arm and let the attending hospitalist know of the result. The patient will then be enrolled in their assigned arm.
- The initial protocol for analgesic administration in each arm is as follows:

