#### B. Statistical Considerations

# a. Sample Size Justification:

- Data from a retrospective study of acute pancreatitis patients receiving either patient-controlled analgesia (PCA, n=116) or conventional IV push (IVP, n=647) showed that mean length of stay was higher in the PCA group (9.9 ± 7.14 days) compared to the IVP group (6.4 ± 9.86 days). The effect size calculated using this data yielded a Cohen's d=0.42. Therefore, assuming a 5% error probability for two groups, the estimated sample size to achieve 80% statistical power was determined to be 87 patients per group. At the midpoint of the study when half of target sample size is reached, preliminary post-hoc analysis will be performed to determine effect size and statistical power.

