# b. Data Analysis:

- Primary and secondary outcomes of interest will be studied as outlined above. Data will be presented as mean ± standard deviation, median [interquartile range; range], and count (percentage), as appropriate. Data will be graphed, QQ plots performed and Shapiro-Wilk test utilized to assess for normality. Statistical tests for primary and secondary outcome will be compared using independent samples t-test and Mann-Whitney U test, as appropriate. Categorical variables were investigated using Pearson's Chi-Square. Statistical significance will be assigned at 0.05. All data will be analyzed using the R statistical software.

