# C. Subject Selection

We will study 174 patients admitted within 24 hours to the hospital with AP between 18 and 65 years of age. Patients will be randomized to receive IV opioids either via PCA (n=87) or PDA (n=87). Exclusion criteria are as follows: known allergy or contraindication to opioids, active illicit drug use, chronic pancreatitis, pancreatic cancer, acute encephalopathy/psychiatric illness that would preclude ability to use PCA, chronic renal insufficiency with a Cr >2, acute renal insufficiency with a Cr >3, and known allergy to acetaminophen or hepatic dysfunction otherwise limiting acteaminophen use.

Inclusion criteria	Exclusion criteria
Diagnosis of AP confirmed by revised Atlanta criteria	Active illicit drug use
	Discharged from the ED
Admitted to the medical floor within 48 hours of ED arrival	Direct admission to ICU from ED
	Known allergy to opioid medications
Age 18-65	Age <18 or >65
	Known chronic pain syndrome or concurrent medical condition with chronic pain
	Active
	encephalopathy/confusion/delirium/psychiatric

Study Description – Part B CCI Form: 9-2015 PI Revision Date: 3/2/2021

illness or any other condition that limits capacity
Known chronic opioid use
Renal insufficiency (baseline Creatinine of >2 and/or AKI with Cr>3 on admission)
Known allergy to acetaminophen or hepatic dysfunction otherwise limiting acetaminophen use

Subjects will be enrolled without regard to race, gender, or vulnerable category status.

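### The primary length-of-stay comparison is unadjusted, although age and admission creatinine are known for every patient at entry: valid, but some precision is given up

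*Combined protocol and SAP*

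**What the plan says.** Section B3.A (Study Design) states that "the patient will be enrolled by simple randomization to either the PCA or the PDA arm of the study". It then says "The research staff will assign patients to either the PCA arm or the PDA arm based on a standard randomization", and describes the mechanics as "the research staff will assign them to the next sequential study ID and corresponding study arm". No blocking, strata or minimisation is mentioned.

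Section B3.B.b (Data Analysis) plans to compare the outcomes by "independent samples t-test and Mann-Whitney U test, as appropriate", after graphs, QQ plots and a Shapiro-Wilk test. It names no covariate.

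Section B3.C (Subject Selection) limits age to 18–65 and excludes "Renal insufficiency (baseline Creatinine of >2 and/or AKI with Cr>3 on admission". Both age and creatinine must therefore be known before a patient is randomised. Section B3.A also has nurses record pain (NRS) and vital signs every 4 hours. It introduces the pain scores as the measure of each arm's efficacy and the vital signs as adverse-event monitoring, and it does not define a pre-randomisation value of either.

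**The concern.** LOS is a very variable outcome. The retrospective source quoted in Section B3.B.a has SDs of 7.14 and 9.86 days on means of 9.9 and 6.4 days. Neither the allocation nor the analysis takes any account of baseline prognosis. If age and renal function at entry predict LOS, an unadjusted test leaves that explained variation in the error term.

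This matters somewhat more here because the plan has no reserve. At the stated effect size, 87 per arm gives slightly less than 80% power. There is no allowance for dropout, and patients who switch arms are to be removed from the analysis. If a baseline imbalance is noticed after the data are seen, any adjustment made then will be open to challenge because none was prespecified.

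**Working it through.** **Inputs.** From Section B3.B.a: Cohen's d = 0.42; "assuming a 5% error probability for two groups"; and "the estimated sample size to achieve 80% statistical power was determined to be 87 patients per group". Sidedness is not stated, and two-sided is assumed. The share of LOS variance explained by baseline covariates (R²) is not in the documents; every value below is an assumption.

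**1. The plan's own figure.** The normal approximation is n per arm = 2(1.960 + 0.842)²/d². With d = 0.42 it gives 89.0; with d = 0.425 it gives 86.9, that is 87. The t-based calculation at d = 0.42 gives 90. So 87 is reproduced to within the rounding of d. Whether 0.42 is the right summary of the source data is a separate question; it is used here as stated.

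**2. Power of the unadjusted test at 87 per arm.** The noncentrality is 0.42 × √(87/2) = 2.770, with 172 degrees of freedom and critical value 1.974. Power is 78.7%.

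**3. Power after adjustment.** Adjustment multiplies the residual SD by √(1 − R²), so the effective d is 0.42/√(1 − R²). The two degrees of freedom spent on two covariates change power by less than 0.01 points.

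| Assumed R² | Effective d | Power at 87 per arm |
|---|---|---|
| 0 | 0.420 | 78.7% |
| 2% | 0.424 | 79.5% |
| 5% | 0.431 | 80.7% |
| 10% | 0.443 | 82.7% |

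**4. R² needed to reach 80%.** With 87 per arm, 80% power needs d = 0.42716. Then R² = 1 − (0.42/0.42716)² = 3.3%.

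**5. Scale.** In the source data the SD-to-mean ratio is 9.86/6.4 = 1.54 in one group and 7.14/9.9 = 0.72 in the other. LOS cannot be negative, so an SD well above the mean points to a long right tail. The table is a t-test calculation on an approximately normal scale. It indicates the relative gain and does not forecast the power of a raw-days regression.

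**6. Does the allocation method itself matter?** With Binomial(174, 0.5), an exact 87/87 split has probability 6.0%, and the central 95% range for one arm is 74 to 100. Power is 77.7% at 74/100 and 78.4% averaged over all splits, against 78.7% at 87/87. The loss is about 1 point at the edge of the range and 0.2–0.3 points on average.

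**The case against.** The strongest reply is that nothing is wrong with the planned test. Randomisation makes the unadjusted comparison unbiased, and its standard error already allows for chance imbalance. That stands, and it limits the point to efficiency.

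A second reply is that the gain may be small. Eligibility narrows both covariates (age 18–65, the creatinine limits), and direct ICU admissions are excluded, so a low R² is plausible. This also stands; hence the 2% row.

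A third reply is that regression on raw days could have less power than the planned Mann-Whitney test when LOS is skewed. That stands too, and is why the scale of the adjusted analysis has to be chosen with care.

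Three stronger readings are tempting, and the documents do not support them:

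- *That simple randomisation fails to deliver the planned arms.* Section B3.C says "Patients will be randomized to receive IV opioids either via PCA (n=87) or PDA (n=87", which reads naturally as a planned number. Study IDs are tied to arms through a list whose construction is not described. Even under pure simple randomisation the cost is about 1 point of power or less. Blocking would not balance severity unless it were stratified, and it adds predictability in a single-centre trial whose arms are visibly different.
- *That severity imbalance biases the LOS result.* For a marker with 30% prevalence (assumption), the standard error of the difference between arms is √(0.3 × 0.7 × 2/87) = 0.069, so a gap of 10 points or more occurs in about 15% of trials. If the marker added 5 days (assumption), that gap would shift the difference by 0.10 × 5 = 0.5 day, against the source difference of 9.9 − 6.4 = 3.5 days. This is random error, not bias.
- *That baseline pain and vital signs are already in hand for every patient.* Patients are recruited on the floor after leaving the ED, and nothing states that a pre-randomisation value is recorded. Only age and admission creatinine can be relied on.

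**Conclusion.** The primary analysis is valid but leaves out two baseline variables that eligibility already requires. Prespecified adjustment would be a cheap improvement, not the correction of an error. Power would rise from 78.7% to about 81–83% if the covariates explain 5–10% of LOS variance, and only to 79.5% if they explain 2%; an R² of about 3.3% would restore the stated 80%. These figures rest on the plan's d = 0.42, 87 analysed patients per arm, a two-sided 5% test, a scale on which LOS is roughly normal, and an R² that the documents do not supply. The randomisation method needs no change on this account.

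**What to change.** In the Data Analysis section, prespecify the primary LOS comparison as a regression on arm adjusted for age and admission creatinine, both entered as continuous variables, with robust standard errors. Fix in advance one scale suited to skewed LOS, for example log LOS or a rank-based adjusted analysis. Keep the unadjusted test as a supportive result. Add the first NRS score and first vital signs only if the sponsor confirms that they are recorded before randomisation for every patient; otherwise leave them out. Settle this before any comparison by arm is seen, including the planned midpoint analysis. In Subject Selection, at most describe 87 per arm as the planned number.

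The cost is a few lines of text and extraction of two values already needed for eligibility. On the log scale the effect is a ratio rather than a difference in days, so a descriptive difference in days should be reported beside it. No extra patients or procedures are needed.

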## **B6. RECRUITMENT AND CONSENT PROCEDURES**

## Recruitment

Patients will be identified as they are admitted to the hospital for management of AP. Our research staff will check with the admitting hospitalists/physicians on a daily basis for patients admitted with AP who may be eligible for enrollment in the study. Once we have identified a patient who meets the study criteria, our research staff will approach the patient and obtain informed consent.

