# Consent

After identifying a potentially eligible inpatient, a study Investigator will fully explain the purpose of this study to the patient. After fully answering the patient's questions and if the patient's consents to entering the study, a signed consent will be obtained. A study investigator will be responsible for obtaining written informed consent from each patient. The patient will be given a copy of the informed consent form, a copy will be placed in the patient's medical record and the original will be kept in the research files.

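### Research staff both recruit patients and assign the arm from a sequential ID, and the plan describes no allocation concealment

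*Combined protocol and SAP*

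**What the plan says.** Three parts of the protocol bear on this.

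- **Assignment (B3.A, Study Design).** "The research staff will assign patients to either the PCA arm or the PDA arm based on a standard randomization". The mechanism is that, after consent, "the research staff will assign them to the next sequential study ID and corresponding study arm", and the attending hospitalist is then told the result. The method is named as simple randomization and is placed after consent: "After obtaining informed consent from the patient, the patient will be enrolled by simple randomization to either the PCA or the PDA arm".
- **Recruitment (B6, Recruitment).** "Our research staff will check with the admitting hospitalists/physicians on a daily basis for patients admitted with AP". Once a suitable patient is found, "our research staff will approach the patient and obtain informed consent".
- **Consent (B6, Consent).** Here the task belongs to someone else: "A study investigator will be responsible for obtaining written informed consent from each patient".

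The protocol does not say who produces the sequence, who keeps it, or in what form staff consult it. It mentions no central or web-based release, envelopes or independent allocator. It describes no blinding.

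**The concern.** Randomization protects against selection bias only if the people deciding whom to enrol cannot know the next assignment. Here each arm is attached to the next ID in an ordered series, and one staff group both finds and approaches patients and performs the assignment. If the ID-to-arm list can be read in advance, staff could pass over a patient, delay an approach or encourage consent more or less strongly, depending on which arm is next.

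Several features of this trial raise the stakes:

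- Some exclusions under Subject Selection call for judgement, such as conditions limiting capacity or liver dysfunction that restricts acetaminophen.
- B4 records an expectation that PCA may improve pain control and shorten stay.
- The hospitalist is told the arm, and no blinding is described.
- The Data Analysis section plans only unadjusted comparisons (t-test, Mann-Whitney U, chi-square), so even a measured baseline imbalance would not be corrected.

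The outcomes exposed are length of stay (primary), pain scores and total opioid dose.

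**Working it through.** **1. Who does what, with the sections side by side.**

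| Step | Who | Where |
|---|---|---|
| Daily search for eligible patients | Research staff, with admitting physicians | B6, Recruitment |
| Approach to the patient | Research staff | B6, Recruitment |
| Consent | Research staff | B6, Recruitment |
| Consent | A study investigator | B6, Consent |
| Assignment from the next ID | Research staff | B3.A |
| Custody of the sequence | Not stated | – |
| Barrier to reading ahead | Not stated | – |

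Whichever consent statement is right, search, approach and assignment stay with research staff. Nothing says that the consenting investigator is kept from the list. The terms simple and standard randomization describe how the sequence is generated, not how it is hidden.

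**2. The plan's own figures, as a yardstick.** The Sample Size Justification gives mean stays of 9.9 days (SD 7.14) and 6.4 days (SD 9.86), and a Cohen's d of 0.42.

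- Planning difference: 9.9 − 6.4 = 3.5 days.
- Common SD as root mean square: √((7.14² + 9.86²)/2) = 8.6 days.
- Sample size at d = 0.42, two-sided 5%, 80% power, normal approximation: 2 × (1.960 + 0.842)² / 0.42² ≈ 89 per group, against 87 stated. That is close enough, and the present point does not depend on it.

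**3. What steering could do (illustration).** The documents give neither the share of patients steered nor how much they would differ. Assume 10–20% of one arm is affected, with a 3–5 day difference in expected stay:

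shift in mean stay = share steered × difference in expected stay

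- 0.10 × 3 = 0.3 days; 0.10 × 5 = 0.5 days
- 0.20 × 3 = 0.6 days; 0.20 × 5 = 1.0 days

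Against the planning difference: 0.3/3.5 = 9% and 1.0/3.5 = 29%.

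**4. Effect on the false-positive rate under the same assumptions.** In SD units the shifts are 0.3/8.6 = 0.035 and 1.0/8.6 = 0.12. With 87 per arm the standard error of the difference, in SD units, is √(2/87) = 0.152. With shift b and no true effect, the two-sided rejection rate is Φ(−1.96 + b/0.152) + Φ(−1.96 − b/0.152):

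- 0.3 days: about 5.6%
- 1.0 day: about 12%

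The inflation is slight at the low end. At the high end it is more than double the nominal 5%.

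**The case against.** A reader might infer that staff know the next arm, or that the allocation is definitely open. The documents do not support that. The wording about the next ID and its corresponding arm fits an open list, but it fits numbered opaque envelopes or an electronic module keyed to study ID equally well. What is established is that no concealment is described.

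Other points in the plan's favour:

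- **Assignment follows consent.** This is good practice and already in the plan. It does not protect the earlier decisions about whom to approach and when if the list is readable beforehand.
- **Simple randomization.** Past assignments do not predict the next, so guessing from the sequence so far is not the risk. The only route is advance sight of the list, and the plan does not close it.
- **A study investigator takes consent.** One part of B6 says so and another says otherwise, so it is not established that one group does everything. The overlap of search, approach and assignment remains.
- **Exclusions narrow the scope.** Active illicit drug use, known chronic opioid use, chronic pain and direct ICU admission are excluded. This limits steering of opioid-seeking or the most severely ill patients, but it leaves variation in severity and expected stay among those eligible.
- **Slow accrual.** At 174 patients in 36 months, about 4.8 a month, with an entry window of 24 or 48 hours (Subject Selection gives both), holding a patient back for a preferred slot is hard. Not approaching a patient remains easy. The 20% figure should therefore be read as an upper illustration, not a forecast.

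**Conclusion.** The point stands as a gap in the design as written. Recruitment and allocation sit with one staff group, arms are tied to sequential IDs, and no safeguard against foreknowledge is described. This goes beyond missing detail, because the plan does set out an assignment procedure and that procedure contains no barrier.

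Actual bias is not shown, and its size cannot be derived from the documents. The 0.3–1.0 day shift (9–29% of the planning difference) and the false-positive rates of about 5.6–12% rest wholly on the assumed 10–20% steered and 3–5 day difference. The rates also assume a common SD of 8.6 days and a normal approximation.

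A reader might also conclude that any such bias would be beyond repair in analysis. That is too absolute: adjustment for measured baseline severity could remove part of it, though not the unmeasured part, and no adjustment is planned. The change should be made, but the point does not by itself invalidate the trial.

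**What to change.** Amend the assignment text in B3.A to state three things:

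1. The sequence is generated and held by someone who takes no part in screening, approach or consent, such as an existing statistician or data manager.
2. Each arm is released only after eligibility and signed consent have been irrevocably logged.
3. Release is through an electronic randomization module or sequentially numbered opaque sealed envelopes.

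Reconcile the two parts of B6 on who obtains consent. If a safeguard of this kind is already used in practice, one sentence in B3.A describing it settles the concealment point.

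The cost is a small set-up effort, with no added patients, visits or staff.
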